The primary objective of the study is to evaluate the impact of a text-message service on smoking cessation in medically underserved, obstetric patients when added to the usual care of pharmacist-driven CBT smoking cessation program and smoking cessation pharmacotherapy with either the nicotine replacement patch or bupropion. The smoking cessation rate will be verified by exhaled carbon monoxide levels (<8ppm) at 2 weeks of the patients quit date. Secondary objectives of the study include (1) a comparison of self-reported cessation versus verified cessation from the exhaled carbon monoxide level, (2) self-reported cessation rates at 1 month, 3 months, and delivery as verified by exhaled carbon monoxide levels, and (3) change in exhaled carbon monoxide levels from baseline to 2 week follow-up, (4), to better understand which patients may face additional barriers with tobacco cessation during pregnancy and ongoing use of marijuana and alcohol may be predictive.

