**Please save frequently**

- c) Describe the study design (e.g., single/double blind, parallel, crossover, control, experimental, observational, etc.). If the study is investigator-initiated, a timeline for individual subject recruitment, follow-up, and analysis for the study is required. Also, indicate if the subjects will be randomized.

**Protocol Title:** Smoking Cessation Following Text Message Intervention in Pregnant Women

---

We propose an 18-month prospective, randomized, open-label evaluation of the impact of texting to pregnant, underserved, cigarette smokers on smoking cessation rates.

March 2014: Obtain IRB approval  
 April 1 2014: Begin enrolling patients via randomization  
 April 31st, 2015: Cease enrollment of new patients  
 June 1st 2015: Final collection of all data for all enrolled patients  
 Summer 2015: Data analysis, manuscript preparation

d) **If subjects will be given placebo, please justify placebo use. \*?HELP?\***

N/A

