#### Follow-up phone calls and visits for Intervention and Control Groups

Usual follow-up includes a telephone call to the patient within 3 days of the quit date then weekly for 2 weeks afterwards. Each phone call includes assessing current smoking status, identifying withdrawal symptoms and how the patient handles them, review of behavior modifications, assessment of reward planning, medication reconciliation, assessment for adherence, concerns, and adverse events with therapy, and education as needed on the above areas.

Patients will be scheduled to return to the Maternal Fetal Care Clinic 2-weeks after their quit date to obtain additional voucher to refill patches or bupropion. At each voucher pick-up, the patient will need to report her smoking status then perform an exhaled carbon monoxide level.

**Protocol Title:** Smoking Cessation Following Text Message Intervention in Pregnant Women

---

Patients will be continued to be seen on a bi-weekly schedule to obtain additional vouchers for patches or for bupropion, meet with the pharmacist, and complete a carbon monoxide exhalation test. These visits will be continued until the pharmacotherapy course is complete.

As the only intervention in this study is text messaging and the primary outcome measure is smoking cessation, we plan to continue the study through the patient's delivery. The patient may discontinue enrollment at any time.

Text Message Intervention  
Smoking Cessation Text Messages

\*Prior to quit date

\*Inform others:

Congratulations, your quit date is in 3 days! Let friends and family know you are planning to quit and how they can help support you. Support is one of the key pieces to quitting smoking!

\* Remove reminders:

Congratulations, your quit date is in 2 days! Get rid of things such as lighters, ashtrays, and cigarettes. Clean your car, house, and clothes so they don't smell like cigarette smoke when you quit.

\*Prepare for cravings:

Congratulations, your quit date is tomorrow! Remember that cravings will only last about 20 minutes, so have activities planned to distract yourself! Do a crossword puzzle, take a walk, clean the house, eat a healthy snack if you're hungry, etc.

\* Reasons why you're quitting

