Congratulations, TODAY is your quit date! Look at the list of reasons you made for quitting and remind yourself of what a great thing you are doing for yourself and for baby! Start using your (patch) today now that you are ready to be smoke free. We are here to answer any questions (phone #)

\* During quit attempt

\*Mid-afternoon of quit date

Starting to have a craving? Go for a brief walk outside and breathe in some nice fresh air! You can do this!!

\* Day 2

Wow! You made it through day 1! Keep up the great work. Remember that cravings don't last more than 20 minutes, so do something fun or work on a project to distract yourself!

\* Day 3

Yeah! 3 smoke free days! Your carbon monoxide level in your blood has decreased to normal, which means your blood oxygen level has increased to normal. More oxygen for you and for baby!

\* Day 5

Have you noticed that your sense of taste and smell has improved? Keep up the great work! Remember that mixing up your routine during the times you used to smoke can help make it easier to stay smoke free!

\* Day 7

Congratulations! You have gone 1 week without smoking! Your body is already benefitting from quitting smoking, such as lower heart rate and blood pressure! Keep up the great work and contact your clinical pharmacists with any questions!

\* Day 10

You are doing great! Remember, if you have a slip up and smoke a few cigarettes, don't be discouraged! This doesn't mean you have failed and should keep smoking—just get back on

**Protocol Title:** Smoking Cessation Following Text Message Intervention in Pregnant Women

---

track right away! Think about what triggered it and how you will deal with it next time. We can help!

\* Day 14

Congratulations! You have gone almost 2 weeks without smoking! Don't forget to pick up your (patches, gum) from the office. You may notice that your lung function and circulation is starting to improve. If you are breathing easier, baby is getting more oxygen too!

\* Day 21

Congratulations! It has been 3 weeks since your quit date! Think about how much money you have saved on cigarettes so far and treat yourself to something special! You may notice less withdrawal symptoms and cravings as well. Keep up the good work!

\* Day 28

Congratulations! You have been smoke-free for almost 1 month! Don't forget to pick up your (patches) from the office.

Check-ins every 2 weeks thereafter

oSimilar reminders every 2 weeks until therapy is complete

Delivery

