Secondary Outcomes-Comparison between self-reported quit rates and verification through exhaled carbon monoxide levels  
Statistical Analysis- McNemar’s

Secondary Outcome-Change in exhaled carbon monoxide levels between baseline and 2 weeks  
Statistical Analysis-Paired t-test

Secondary Outcome-Comparison for demographics and verified cessation rates at 2 weeks  
Statistical Analysis-Parametric: t-tests, Nonparametric: Chi-squared or Fisher’s exact

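### McNemar's test is a weak sole analysis of self-reported against CO-verified cessation: define the term and report the proportion of reported quits that CO does not confirm

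*Combined protocol and SAP*

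**What the plan says.** Secondary objective (1) in section 2(b) is "a comparison of self-reported cessation versus verified cessation from the exhaled carbon monoxide level". The matching entry under Outcomes and Statistical Analysis in section 3(d) is "Comparison between self-reported quit rates and verification through exhaled carbon monoxide levels", and the analysis given for it is only "Statistical Analysis- McNemar"'s test. The entry names no exact or asymptotic version, time point, estimate, confidence interval, agreement measure or arm contrast.

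The data are paired. Under the follow-up visits in section 3(b), at each voucher pick-up "the patient will need to report her smoking status then perform an exhaled carbon monoxide level".

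Two sentences in section 2(b) bear on what verified cessation means. The primary one reads "The smoking cessation rate will be verified by exhaled carbon monoxide levels (<8ppm) at 2 weeks of the patients quit date", which fits CO below 8 ppm as the criterion by itself. Secondary objective (2) reads "self-reported cessation rates at 1 month, 3 months, and delivery as verified by exhaled carbon monoxide levels", which fits a reported quit that CO then confirms. The plan does not choose between them.

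**The concern.** The reason to collect CO beside self-report is to learn how far a reported quit can be trusted. A reader of the results will want to know what fraction of reported quits CO fails to confirm, and how precisely that fraction is known. A lone McNemar p-value gives neither.

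Under one definition the p-value is a function of a single count. Under the other, a large p-value can sit beside substantial disagreement and be misread as support for self-report. At stake is the interpretation of secondary objective (1), and of any self-reported cessation rate quoted alongside it.

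**Working it through.** **Inputs.** Alpha 0.05 (sidedness not stated; two-sided assumed), 52 patients, 60 after allowance for 15% loss, and 30% expected cessation at 2 weeks, all from section 3(d). These were set for the primary comparison. The plan gives no power, discordance rate or false-report rate for the McNemar analysis, so there is no planned figure to reproduce. Every cell count below is an assumption for illustration.

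**Notation.** Let *b* be the number of women who report quitting but have CO ≥8 ppm, and *c* the number who report smoking but have CO <8 ppm. The exact two-sided McNemar p is twice the upper tail P(X ≥ max(*b*, *c*)), with X ~ Binomial(*b*+*c*, 0.5), capped at 1.

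**Combined definition (reported quit plus CO <8 ppm).** A woman who reports smoking cannot be a verified quitter, so *c* = 0 by structure and p = 2 × 0.5^*b* for *b* ≥ 1.

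- *b* = 5: 2 × 0.03125 = 0.0625
- *b* = 6: 2 × 0.015625 = 0.031
- *b* = 10: 2 × 0.5^10 = 0.002

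The number of reported quitters does not enter. Six unconfirmed among 16 reported quits (37.5%) and six among 22 (27.3%) both give p = 0.031. The unnamed version of the test also matters. With *c* = 0 the uncorrected chi-square equals *b*, so *b* = 4 already gives p = 0.046. With the continuity correction the statistic is (*b*−1)²/*b*, giving p = 0.074 at *b* = 5 and 0.041 at *b* = 6.

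The chance of reaching *b* ≥ 6 among 52 women, if 5%, 10%, 15% or 20% of all women made an unconfirmed quit report (assumed range), is 4.5%, 42%, 81% or 96%.

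**CO-alone definition (CO <8 ppm).** Here *c* can exceed zero and the test compares the two paired rates. With 60 × 0.85 = 51 women, take *b* = 5 and *c* = 5. Then 10/51 = 20% are classified differently by the two measures, yet the doubled tail is 2 × 0.623, capped at p = 1.0.

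The next table uses 52 women, with both rates fixed at 16/52 = 31%, and lets the disagreement grow:

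| *b* = *c* | Reported quits with CO ≥8 ppm | Kappa | McNemar p |
|---|---|---|---|
| 0 | 0/16 = 0% | 1.00 | 1.0 |
| 5 | 5/16 = 31% | 0.55 | 1.0 |
| 10 | 10/16 = 62.5% | 0.10 | 1.0 |

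Kappa for the middle row: observed agreement 42/52 = 0.808; chance agreement (16² + 36²)/52² = 0.574; (0.808 − 0.574)/(1 − 0.574) = 0.55.

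The test does respond when errors run one way: *b* = 6, *c* = 0 (16/52 against 10/52) gives p = 0.031.

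**Precision by arm.** At 30% of 51, about 15 women report quitting, or roughly 8 per arm. An assumed 2/8 unconfirmed has an exact 95% interval of about 3% to 65%.

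**The case against.** The strongest defence is that the listed outcome compares quit rates measured twice in the same women, and McNemar's test is the standard test for equality of paired proportions. That stands under the CO-alone definition. A reader might infer that the test is wrong under either definition; the documents do not support this. The limitation there is that equal rates are not the same thing as agreement.

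A reader might also infer that, under the combined definition, the null hypothesis is false by construction. It is not. If every reported quit is confirmed, *b* = 0 and p = 1. The accurate statement is that the null reduces to there being no unconfirmed reports, and the p-value reflects only their count.

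A third tempting inference is that the plan pools the arms and wrongly omits a comparison of false reporting between them. Section 3(d) does not say whether the test is pooled or run by arm, and no objective asks for that contrast. There is some reason for interest: section 2(c) describes the evaluation as open-label, and only the texting arm receives messages that presume abstinence, such as "You have gone 1 week without smoking". A McNemar test has no arm term and could not address this. But the comparison would condition on having reported a quit, a subset formed after randomisation, and would be very imprecise. It is an optional addition and its absence is not an error.

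Finally, this is one secondary outcome in a self-described pilot, and the equal-and-opposite split is a chosen extreme. Both remarks are fair, and they limit the weight of the point.

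**Conclusion.** The point holds as a minor one. McNemar's test is a weak sole analysis for secondary objective (1), because verified cessation is not defined and the test yields neither the unconfirmed proportion nor a measure of agreement under either definition. Under the combined definition the exact p is fixed by one count (0.063 at 5 unconfirmed reports, 0.031 at 6). Under the CO-alone definition the test is valid for equality of rates but can return p = 1.0 with 20% of women classified differently. The algebra does not depend on the assumed counts; the sizes do, since the plan gives no false-report rate.

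A reader might extend this to the primary result. The documents do not support that: the primary outcome requires CO below 8 ppm, so a false report alone cannot turn a woman with CO at or above 8 ppm into a primary success.

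**What to change.** In section 3(d):

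1. State whether verified cessation means CO <8 ppm alone or a reported quit plus CO <8 ppm, and name the time point of the comparison.
2. Show the 2×2 table of self-report by CO.
3. Make the main result the proportion of self-reported quitters with CO ≥8 ppm, with an exact 95% confidence interval.
4. Keep McNemar's test only as a supplement under the CO-alone definition, and name the exact version.
5. Optionally, show the same proportion by arm with the difference and its confidence interval, labelled exploratory and conditional on a reported quit.

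The cost is wording only, because both measurements are already taken at the same visits. The downside is wide intervals, since few women are expected to report quitting. The Expedited Paragraphs section marks the remaining activity as limited to data analysis, so the change is still possible but should be dated and described as made at that stage.

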groups. We will use a random number generator to help with patient randomization. These numbers will be placed in a sealed envelope and shuffled. At the time of patient inclusion, an envelope will be selected by the pharmacist. However, if a patient declines receiving text messages but consents to participate in the pharmacist driven CBT and NRT, she will be enrolled in the standard of care group. A baseline carbon monoxide level will be obtained.

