#### Description of Usual Care

The patient, regardless of group, will have the standard of care smoking cessation visit with the clinical pharmacy specialist or PGY2 ambulatory care resident. The visit will include

- Medication reconciliation
- Review social history which includes use of street drugs and alcohol, allergies, and vaccine history
- Obtain smoking history that included current amount smoking, changes in smoking habits during this pregnancy, number of years smoked, quit attempt history, and use of previous smoking cessation aids
- Design a quit plan that includes setting a quit date within the next 30 days, obtain follow-up contact information, identify motivators/triggers/barriers, discuss withdrawal symptoms, develop plan for management of withdrawal symptoms, develop a plan for behavior modifications, discuss rewards, handling of relapse, medication options for cessation during pregnancy, and education on purpose, proper use, potential maternal and neonatal adverse events

If the pharmacist, physician, and patient deem that pharmacotherapy is appropriate, the patient will receive a 2 week supply if using NRT or 3 week supply if using bupropion. The smoking cessation pharmacotherapy will be supplied free of charge to the consenting participants. If the patient is prescribed NRT patches, the medication will be provided in two week intervals. If the patient is prescribed bupropion, the medication will be provided for a 3 week supply with the initial dispensing and 2 week supply thereafter. Dosing and length of treatment will follow package insert approved dosing. Patients will receive a voucher to take to the Clayton Health Services Pharmacy located across the street from the Maternal Fetal Care Clinic to receive either medication at no cost.

Demographics, social history, gestation age at enrollment, estimated due date, medications at enrollment, past medical history, and obstetric history include gravity and parity will be obtained from the EPIC medical record. Patients will be asked about smoking history, time to first morning cigarette, previous quit attempts, previous experience with cessation pharmacotherapy, motivators, triggers, and barriers during initial visit.

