If available, delivery details will be abstracted from the patient charts and shall include gestational age at delivery, fetal weight, APGAR scores, and umbilical cord gases.

- c) **If the proposed study is a clinical trial where a drug, vaccine, device or other treatment is compared to a placebo group or comparison treatment group, what are the guidelines or endpoints by which early decisions regarding efficacy or lack of efficacy can be made? For example, it may be reasonable to stop enrollment on a study when efficacy has already been clearly demonstrated, to avoid unnecessary enrollments of additional subjects. Alternatively, it may be reasonable to stop enrollment when it is clear that efficacy will never be demonstrated, given the statistical power of the study as designed. Describe the guidelines that are in place to assist in making these determinations, if relevant to the proposed study.**

N/A

- d) **Describe how data analysis will be performed (statistical tests, methods of evaluating data) and indicate the smallest group/unit for which separate reporting will occur. For studies involving a questionnaire, if data and reliability information are available, please describe or provide references. For full board, unfunded studies describe sample size determination and power analysis. If none, please justify.**

Power Calculation

Based on previous experience, we anticipate 30% of patients will stop smoking at 2 weeks and anticipate texting will increase cessation rates by an additional 5%. Using G\*Power, based on a Chi square test, alpha of 0.05, power of 0.8, and medium effect size of 0.5, we estimate needing 52 patients. We anticipate 15% lost to follow-up or drop outs, so we anticipate needing 60 patients for this pilot project.

G\*Power is a free online statistical tool for calculating power in social, behavioral, and biomedical sciences.

Outcomes and Statistical Analysis

Primary Outcome- Smoking cessation rate verified by exhaled carbon monoxide levels (<8ppm) at 2weeks of quit date between texting and control group

Statistical Analysis- Chi-squared or Fischer's Exact Adjusted for confounders: multiregression

**Protocol Title:** Smoking Cessation Following Text Message Intervention in Pregnant Women

---

Statistical Analysis- Chi-squared or Fischer’s Exact Adjusted for confounders: multiregression analysis

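### Change in exhaled carbon monoxide is analysed only by a before-after paired t-test with no arm term, so the planned analysis cannot show an effect of texting

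*Combined protocol and SAP*

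**What the plan says.** Section 3d (Outcomes and Statistical Analysis) defines the outcome as "Secondary Outcome-Change in exhaled carbon monoxide levels between baseline and 2 weeks" and gives one line of method, "Statistical Analysis-Paired t-test". The matching item in section 2b, secondary objective 3, is "change in exhaled carbon monoxide levels from baseline to 2 week follow-up". Neither names the arms, and 3d does not say whether the test is pooled over all women or run within each arm.

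Three other places bear on this:

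- The aim in 2b is to "evaluate the impact of a text-message service on smoking cessation". The primary outcome in 3d is worded as a comparison of arms, "at 2weeks of quit date between texting and control group". The regression adjustment is listed under that binary outcome only.
- Usual care is common to both arms. Section 3b states: "The patient, regardless of group, will have the standard of care smoking cessation visit". That visit sets a quit date, and medication follows where it is judged appropriate. In the power calculation the investigators "anticipate 30% of patients will stop smoking at 2 weeks and anticipate texting will increase cessation rates by an additional 5" percent, so most of the expected quitting does not depend on texting.
- The readings for a comparison of arms are already planned. In 3b, "A baseline carbon monoxide level will be obtained", and CO is measured again at the visit two weeks after the quit date.

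No other section analyses change in CO.

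**The concern.** A paired t-test asks whether CO fell. In smokers who have agreed to quit and are being helped to do so, CO will probably fall in both arms. A significant result would correctly answer that question and say nothing about texting.

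Two things are at stake. First, baseline and 2-week CO are collected in a randomised trial, yet the plan draws from them no estimate of the texting effect on the CO scale. Second, a small p-value for this outcome, printed in a report about text messaging, could be read as support for texting when usual care alone would have produced it.

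**Working it through.** The plan gives no sample size, SD or effect for CO change, so there is no figure of its own to reproduce. The check is on what the test responds to.

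**1. What the test estimates.** Let D_T and D_C be the mean falls in CO in the texting and control arms. With equal arms, the pooled paired test concerns (D_T + D_C)/2. The effect of texting is D_T − D_C. The first can be large when the second is zero.

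**2. Standardised check.** Inputs: 52 women (3d) and two equal arms (3b), so 26 per arm. The SD of change is set to 1 and the falls are assumed.

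- Fall of 0.5 SD in both arms, no texting effect: the pooled noncentrality is 0.5 × √52 = 3.61. The paired test rejects in 94% of trials and a between-arm t-test in 5%.
- Fall of 0.8 SD in both arms: the paired test rejects in more than 99.9%, the between-arm test in 5%.
- Texting worse than control (falls of 0.3 and 0.8 SD): the paired test still rejects in 97%.

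**3. Running it by arm.** With a common fall of 0.5 SD, each arm of 26 is significant with probability 0.688. Exactly one arm is significant with probability 2 × 0.688 × 0.312 = 0.43, although texting does nothing. In the null CO simulations below, at 30% quitting, this happens in 25% to 50% of trials.

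**4. CO-scale simulation, no texting effect.** All CO values are assumptions:

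- Baseline is lognormal with median 13 or 20 ppm and log-SD 0.5.
- Quitters at 2 weeks are lognormal with median 3 ppm and log-SD 0.4.
- Non-quitters have baseline × exp(N(μ, 0.3)).
- There are 4,000 trials per cell, so the Monte Carlo standard error is at most √(0.25/4000) = 0.8 points.

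Entries are the proportion of trials in which the pooled raw-scale paired test (two-sided 0.05) shows a significant fall.

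| Baseline median | Quit rate, both arms | μ = −0.1 | μ = −0.045 | μ = 0 | μ = +0.1 |
|---|---|---|---|---|---|
| 13 ppm | 30% | 0.975 | 0.881 | 0.725 | 0.302 |
| 13 ppm | 20% | 0.870 | 0.624 | 0.395 | 0.053 |
| 13 ppm | 10% | 0.603 | 0.248 | 0.070 | 0.001 |
| 20 ppm | 30% | 0.980 | 0.923 | 0.791 | 0.370 |
| 20 ppm | 20% | 0.891 | 0.674 | 0.418 | 0.069 |
| 20 ppm | 10% | 0.640 | 0.285 | 0.094 | 0.004 |

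μ shifts the median of non-quitters. Their mean is multiplied by exp(μ + 0.3²/2), so it changes by about −5%, 0%, +5% and +16% across the four columns. The phrases *cut down about 10%* and *rises about 10%* therefore describe medians.

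The direction can be checked by hand for median 13, 30% quitting and μ = 0. The baseline mean is 13 × exp(0.125) = 14.73. The quitters' mean is 3 × exp(0.08) = 3.25. The 2-week mean is 0.3 × 3.25 + 0.7 × 14.73 × exp(0.045) = 11.76. The expected fall is thus 2.97 ppm with no texting effect.

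**5. Between-arm ANCOVA on the same data.**

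- Null (median 13, μ = 0, quitting 10% to 30%): rejects in 5.0% to 5.4% on log(CO + 1) and 5.0% to 5.2% on the raw scale.
- 30% versus 35% (median 13, readings rounded to whole ppm, μ = 0, −0.045, −0.1): rejects in 6.0% to 6.7% on log(CO + 1) and 5.4% to 6.1% on the raw scale.

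With 26 per arm and 80% power, the smallest detectable difference in change is 0.79 SD of change. With ANCOVA and a baseline to follow-up correlation of 0.3, 0.5 or 0.7, it is about 0.76, 0.69 or 0.57 SD of 2-week CO.

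**6. Calibration.** At 30% quitting and μ = 0, the share below 8 ppm goes from 3% at baseline to 34% at 2 weeks for median 20, and from 17% to 44% for median 13. Median 20 is the closer match to the plan's 30%, and its paired-test figures are the slightly higher ones.

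**The case against.** The strongest reply is that the test suits its objective. Secondary objective 3 asks only about change over two weeks, and a paired t-test is valid for that. The other secondary analyses in 3d are not worded as arm comparisons either, so the set may be meant as descriptive. Texting is already tested on CO through the primary outcome, which compares CO-verified cessation between arms at the same visit. The trial calls itself a pilot, and the proposed replacement has almost no power at the planned effect.

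Much of this is true. The paired test does match the literal wording, the primary comparison is unaffected, and only the continuous-scale estimate is missing. But the whole study is framed as an evaluation of texting, and this analysis gives no information on it. Low power is no reason to test something else: a wide interval around the right quantity is useful in a pilot, and a p-value for a different question does not replace it.

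If the test were run by arm, a difference could be computed from the two sets of results, but the plan specifies no such contrast. Setting two within-arm p-values side by side is not a test of it.

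Two limits stand. The simulated percentages rest on assumed CO values and range from under 1% to 98%. Also, only the texting arm is texted about refills, and CO is measured when vouchers are collected, so attendance may differ by arm. Complete-case ANCOVA is exposed to that; so are the paired test and the primary outcome.

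**Conclusion.** The concern holds. As planned, the CO-change analysis cannot estimate or test the effect of texting, whether pooled or run by arm. That follows from the form of the test and needs no assumed values.

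How often it would mislead does depend on assumptions. With no texting effect and the plan's 30% quitting, the pooled test shows a significant fall in 73% to 98% of trials if non-quitters hold steady or cut down, and in 30% to 37% if their CO rises. At 20% quitting the ranges are 40% to 89% and 5% to 7%. At 10% they are 7% to 64% and under 1%.

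This concerns one secondary outcome in a pilot. It should be corrected, but it does not touch the primary analysis.

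**What to change.** In 3d, replace the paired t-test with a between-arm comparison: 2-week CO regressed on allocated arm and baseline CO. Restrict it to randomised women, because 3b places women who decline texts in the standard-of-care group without randomisation. Choose log(CO + 1), which keeps zero readings defined, or the raw scale, and fix the choice before analysis. Report the adjusted arm effect with its 95% CI and a rank-based check. Show within-woman change by arm as description only, without comparing p-values across arms. Report the number with a 2-week reading in each arm.

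The cost is one or two lines of text and no new data. A rule for zero readings is needed, and the analysis still uses only women with a 2-week reading. The continuing-review entry marks the remaining activities as limited to data analysis. If CO results have already been examined, the comparison should still be reported and labelled as added afterwards.
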